## 4.0 Design Considerations.

**Justification for Sham Acupressure and No Treatment Arms.** We chose to add a sham acupressure arm to this study so that we had a control arm that could be blinded to participants and study staff. Sham acupressure also controls for placebo (non-specific) effects associated with acupressure, and thus will allow us to estimate the specific or true effects of the relaxing acupressure treatment. The no treatment arm controls for regression to the mean and is an accurate reflection of what the majority of cancer survivors are receiving for their persistent fatigue from health care providers—no treatment.

**Justification for Acupressure Dose (3 minutes per acupoints) and Duration (6 Weeks).** In our original

acupressure pilot study in adult cancer patients, we found that, regardless of treatment arm, the number of minutes performing acupressure was significantly correlated with reduction of fatigue or sleepiness. Participants (per their study logbooks) who stimulated their points for shorter periods of time, i.e., 1 minute, had less of an effect on fatigue and sleepiness compared to those who stimulated their points for 3 minutes. We also determined, from pilot work with fatigued cancer patients assigned to self-administered acupressure for 12 weeks, that change in fatigue improved over 6 weeks and then plateaued, with no further significant improvement. Finally, our preliminary data from our randomized controlled trial in fatigued breast cancer subjects demonstrated improvements in subjective fatigue outcomes at 6 weeks.

**Justification for 24-Week Follow-up.** Our pilot data in fatigued adult breast cancer patients demonstrates that our 6-week acupressure intervention has sustained effects on fatigue, sleep and quality of life outcomes up to 4 weeks after the cessation of the acupressure treatment. Other acupuncture interventions mainly in chronic pain populations have seen sustained effects ranging from 6 months to one year post-intervention and similarly, behavioral therapies for fatigue have sustained impacts of from 24 to 26 weeks (6 months). For acupressure to be a widely used and implemented treatment we would need to observe sustained effects on fatigue reduction of the intervention similar to other pain treatments. As such, we are proposing a 24-week post-treatment follow-up for this study.

#### **4.1 Study Measures.**

Table 2 lists all study procedures and indicates with an 'x' during which visit a particular procedure is performed.

**Table 2**

	Screening phone call	Baseline Week 0	Treatment Phase Weeks 1 - 6	Follow-up Week 6 (- 2 days/+5 days)	Follow-up Week 12 (- 2 days/+5 days)	Follow-up Week 24 (- 2 days/+5 days)
Phone Screen	X					
Screening Survey	X					
BFI	X	X		X	X	X
PHQ-2	X					
Consent	X					
Pt. Info & Dem.	X					
Concomitant of Medications		X				
Diagnosis & Treatment of initial cancer		X				
FACT-O		X		X	X	X
PSQI		X		X	X	X
PROMIS		X		X	X	X
IPAQ		X				
SCQ		X				
FSQ		X				
MAIA		X		X		
Daily Logbook			X			
Acupressure Fidelity				X		
Assessment of blinding				X		
AcuWand Comfort				X		
Final Evaluation						X

**Administering Study Assessments.** All potential participants will be screened over the phone using a brief questionnaire to confirm eligibility for the study. Enrolled participants will then receive an email link to their RedCAP study measures at baseline, weeks 0, 6, 12 and 24. All the surveys will be administered at all-time points with the exception of descriptive and baseline assessments, which will only be collected at week 0; fidelity, blinding and adherence, which will only be asked at week 6; and a final evaluative questionnaire about the participants' perception of the study and the use of the AcuWand device. Adverse events will be collected at all-time points. Inspirational reminder emails, texts, or phone calls (as appropriate for a given participant) will be made to encourage the highest possible response rate to each round of study assessments. Participants without an email account will be assisted in obtaining a free Gmail account and how to access it on their computer tablet by study staff. Those participants who do not have access to Wi-Fi will be assisted in finding free Wi-Fi in their community (e.g., public library, Starbucks, McDonalds, etc.) IT study staff will be available to assist participants with any questions that may arise. E-mail is required so that study instruments may be accessed through surveys in RedCAP.

**Screening.** All potential participants will be screened over the phone using a basic questionnaire to confirm their eligibility. Specifically, an abbreviated form of the *Patient Health Questionnaire (PHQ-2)* will be used to detect untreated depression, and the *Brief Fatigue Index (below; BFI)* will be used to determine fatigue. These measures will be collected before consent and enrollment in to the study and will therefore be kept to the absolute minimum to determine eligibility.

Rescreening. Participants may be rescreened at 6 weeks after initial screening if they failed their initial screening based on: stable chronic medications and no new planned interventions for their fatigue or cancer.

**Fatigue Measure (administered at screening and weeks 0, 6, 12, 24).** *Brief Fatigue Inventory (BFI)* will be used to assess the severity and impact of fatigue on daily functioning. The BFI is a scale validated in cancer patients with an alpha coefficient exceeding 0.95, which correlates well with other fatigue measures. The BFI assesses severity and impact of fatigue in cancer patients over the past 24 hours. The instrument consists of 9 items, each measuring fatigue on a 0-10 scale, and is calculated from the mean of completed items. Scores of  $\geq 4$  indicate clinically- relevant fatigue. A three-point change or a drop below 4 is considered a clinically meaningful change.

**Sleep Quality (administered weeks 0, 6, 12, 24).** *Pittsburgh Sleep Quality Index (PSQI)* is widely used 19-item questionnaire evaluates sleep disturbance over the past month. It yields a total score and 7 component scores: sleep quality; sleep latency; sleep duration; habitual sleep efficiency; sleep disturbances; use of sleep-promoting medication; and daytime dysfunction. In women with breast cancer, Cronbach's alpha for the global PSQI is 0.80. A score  $>7$  in breast cancer patients and thus likely in ovarian cancer patients suggests poor sleep quality. The scale has adequate psychometrics. The primary outcome will be the total PSQI score at baseline and week 6, although we will conduct exploratory analyses on the PSQI subscales.

**Quality of Life (administered weeks 0, 6, 12, 24).** *The Functional Assessment of Cancer Therapy Ovarian (FACT-O)* is a multidimensional questionnaire developed and validated for use by ovarian cancer patients; it includes the 27-item FACT-General (FACT-G) targeted to general cancer patients and 12 questions specific to issues faced by ovarian cancer patients (FACT-O subscale). The FACT-G questionnaire includes the following four subscales: physical well-being (PWB; seven items), social well-being (seven items), emotional well-being (six items) and functional well-being (FWB; seven items). These subscales can be analyzed separately or aggregated to produce a total health related quality of life score. The FACT-G has demonstrated reliability, validity and responsiveness to change over time. Two of the FACT-G subscales (PWB and FWB) plus the FACT- O subscale are summed to represent the total quality of life score.

**Symptoms Associated with Fatigue (administered weeks 0, 6, 12, 24).** We will be using Patient Reported Outcomes Measurement Information System (PROMIS) measures. To diminish participant burden, we will be using the short form versions of these measures. In a study in head and neck cancer patients a PROMIS battery asking about physical function, fatigue, sleep disturbance, depression, negative perceived cognitive function **took only 6.2 minutes to complete**. The validity of PROMIS instruments has been assessed in both general and

clinical U.S. sample populations including oncology populations. PROMIS short forms represent the items of the PROMIS item banks constructed to measure the targeted constructs. All of the included PROMIS forms use 5-point Likert-type response categories to capture intensity, frequency, or duration, described in detail below. Most

instruments use a seven-day recall period, with the exception of PROMIS Sexual Function and Satisfaction Profile which has a 30-day timeframe. PROMIS instruments are publicly available on the PROMIS Assessment Center Library website. Following are detailed description of our included measures.

**PROMIS Short Form v1.0 - Emotional Distress- Anxiety 7a** measures “fear, anxious misery, hyperarousal, and somatic symptoms related to arousal”. The instrument consists of 7 items that ask respondents about the frequency with which they experienced emotions such as fear, stress, and anxiety (“never” to “always”). Scores range from 36.3 to 82.7 with higher scores indicating worse anxiety.

**PROMIS Short Form v1.0 - Emotional Distress - Depression 8b** measures “negative mood, decrease in positive affect, information processing deficits, negative views of the self, and negative social cognition”. It consists of 8 items in which respondents indicate the frequency with which they have experienced emotions such as worthlessness, hopelessness, and sadness (“never” to “always”). Scores range from 35.2 to 82.4 with higher scores representing worse depression.

**PROMIS Short Form Sexual Function and Satisfaction Profile v1.0 – Female** - A collection of 11 brief(1-3) item short forms assessing interest in sexual activity, orgasm, global satisfaction with sex life, lubrication, and vaginal discomfort. The profile is intended for broad use, although almost all of the development work was with cancer populations. Scores range from 25.2 to 84.4 with higher scores representing worse sexual function.

**PROMIS Short Form v1.0 - Sleep Disturbance 8b** This is an 8 item measure of perceptions of sleep quality, sleep depth, and restoration associated with sleep. Scores range from 28.9 to 76.5 with higher scores representing worse sleep disturbance.

**PROMIS Short Form v1.0 - Pain Interference 8a** measures “impact of pain on physical, mental, and social activities”. It consists of 8 items measured on a 5-point Likert-type scale (first 5 questions: “not at all” to “very much”; final question: “never” to “always”). The questions assess the degree to which pain interferes with enjoyment in life, ability to concentrate, day-to-day activities, recreational activities, tasks away from home, and socializing with others. The scores range from 41 to 78.3 with higher scores representing worse pain impact.

**PROMIS Short Form v2.0 - Cognitive Function 8a** measures “mental acuity, concentration, verbal and nonverbal memory, verbal fluency, and perceived changes in these cognitive functions. The extent to which cognitive impairments interfere with daily functioning, whether other people observe cognitive impairments, and the impact of cognitive dysfunction on quality of life are also assessed. Scores range from 14.7 to 68.6 with higher scores representing worse cognitive function.

**Multidimensional Assessment of Interoceptive Awareness (administered weeks 0, 6).** *The Multidimensional Assessment of Interoceptive Awareness (MAIA)* is a multidimensional questionnaire developed as a self-report measure of interoceptive body awareness. The MAIA includes an 8-scale state-trait questionnaire with 37 items to measure multiple dimensions of interoception by self-report. Participants score each answer on a range from 0 to 5 with total scores being calculated using the included rubric.

### **Descriptive/Baseline Variables (administered week 0).**

*Fibromyalgia Symptom Questionnaire (FSQ)* consists of an assessment of widespread pain and symptom severity. The Widespread Pain Index (WPI) assesses the 19 specific body areas described in the survey criteria with scores ranging from 0-19. The second aspect of the criteria will be evaluated using the Symptom Severity (SS) scale (score 0-12). As per the survey criteria, patients will be classified as fibromyalgia positive (FM+) if their scores were WPI  $\geq 7$  and SS  $\geq 5$  or WPI = 3-6 and SS  $\geq 9$ . The validity of the survey criteria has been established both when compared with the 1990 ACR criteria (which included the tender point examination) and the 2010 preliminary diagnostic criteria which include physician assessment.

*Concomitant Medications* including dose, duration/frequency of use, and reason for use will be recorded.

Sociodemographic Variables will include, but not be limited to: date of birth, race, ethnicity, marital status, education, and annual household income.

Cancer Diagnosis and Treatment. We will collect information about cancer treatments and diagnoses. These will be cross validated with data from the tumor registry.

Physical Activity. Because physical activity is known to impact the presence and severity of cancer-related fatigue and sleep disturbance we will collect participants' activity using *The International Physical Activity Questionnaire (IPAQ)*. The IPAQ assesses self-reported physical activity via a validated 7-day recall measure in which time and frequency spent performing activities of different intensities are recorded and tallied.

Obesity and related comorbid conditions may also increase risk for common adverse cancer treatment effects, including fatigue, poor health-related quality of life, and worse functional health. As such, we will be collecting:

Comorbidities using the *Self-Administered Comorbidity Questionnaire (SCQ)*. The SCQ is based on Katz's validated self-report adaptation of the Charlson Comorbidity Index to measure the presence and/or history of several chronic health conditions.

Body Mass Index (BMI) using a modified version of an e-health anthropometric questionnaire that includes questions dealing with self-measurement of current height, weight and has been found to highly correlate with in-person height and weight measurements.

**Safety, Fidelity, Blinding and Adherence (administered week 6 except for adverse events and adherence to acupressure, which are collected throughout the study).**

Adverse Events will be graded according to National Cancer Institute Common Toxicity Criteria version 4.03.

Testing Participant Fidelity We will be assessed using two methods. The first, as detailed in our prior study, is done by research staff using a Skype face-to-face call (we will install Skype on the computer tablets and assist participants in using this program as needed.) Participants will be asked to identify the location, stimulation technique, and the amount of pressure (be able to demonstrate correct use of their AcuWand) of their acupoints. The number of acupoints correctly located will be recorded as will the adequacy of stimulating the acupoints (recorded as "yes" or "no"). The percentage of correct answers 0 to 100% will be calculated, based on circular (clockwise or counterclockwise) motion, maintaining contact with skin, and applying pressure such that the nail of the applying finger/thumb blanches. The second method will be data download from the AcuWand via Bluetooth when the computer tablet is connected to Wi-Fi. The AcuWand will be able to provide data on the duration, frequency, and amount of pressure used by participants-it cannot provide data on the location of where participants stimulated their points. We employ both methods to ensure that fidelity is measured across all parameters and in collect redundant measure in case an AcuWand does not transmit data.

Blinding will be assessed by asking participants, which type of acupressure they thought they were performing.

Adherence to Acupressure will be assessed by asking participants to record if and when they performed acupressure, the order in which they performed their acupressure points, and the amounts of achiness and/or tenderness they experienced while performing the acupressure on a Visual Analog Scale daily in the study logbooks. These will be used in association with data downloaded from the AcuWands. Bi-weekly emails will be used to troubleshoot and encourage adherence.

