## 1.0 BACKGROUND AND SIGNIFICANCE

**Fatigue and Ovarian Cancer.** Women diagnosed with ovarian carcinoma (cancer) report multiple quality of life challenges, including persistent fatigue and sleep disturbances. Persistent fatigue is a commonly reported symptom in these women, with as many as 30 to 60% of ovarian cancer survivors continuing to report significant fatigue even several years after the end of treatment. In ovarian cancer, persistent fatigue has been linked to higher levels of chronic pain, lower quality of life, and reduced participation in other self-care activities such as physical activity. Interestingly, risk factors for fatigue post cancer treatment does not appear to be associated with type of cancer, cancer treatment, stage of diagnosis or histopathology of the cancer, but instead with other host factors such as presence of depression or level of physical activity. While the etiology of persistent fatigue in cancer survivors is unknown, recent research in female cancer survivors suggests that cancer related fatigue may involve pathology within the brain, and thus treatments that target the brain may have promise for treating fatigue. Despite the challenges caused by persistent fatigue, there have been very limited attempts to identify self-care-focused interventions, which could improve fatigue, sleep, and quality of life among ovarian cancer survivors. We are proposing to carry out a randomized, controlled trial comparing self-administered acupressure to sham acupressure and no treatment to determine if this is an intervention that survivors can use to address their fatigue.

[figure not shown]

**Figure 1.** A plot of mean weekly fatigue scores for relaxing acupressure (red circles), High Intensity Stimulating Acupressure (closed black circles), and Low Intensity Stimulating (open circles) across study weeks

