### Statistics Section.

The primary aim of this study is to investigate the differential effects of different modes of acupressure (relaxing vs. sham vs. no treatment) on fatigue as measured by the BFI in ovarian cancer survivors at week 6. The BFI, which measures the average degree of fatigue, gives a score that ranges between 0 and 10, with higher numbers indicating more fatigue. To investigate the difference in BFI between the three study arms, we shall use linear mixed-effects regression analysis with BFI as outcome, *week* as the within-subjects factor with four levels (0, 6, 12, 24) and *group* (relaxing acupressure, sham acupressure, no treatment) as the primary between-subjects factor. Of interest is the group-by-week interaction (to be included in the model), significance of which will indicate differences in extent of decrease between the arms. The covariate cancer stage at diagnosis and the interaction term group-by-stage will be added to models. Post-hoc sliced main effect of weeks within each study arm will be estimated. A *subject* random-effect will be used to account for the clustering effect within the four measurements on the same subject. Model diagnostics will be carried out to confirm the distributional assumptions and appropriate corrective actions (e.g. transformation) will be performed as needed. Models with more flexible covariance pattern (e.g. unstructured covariance, heterogeneity across groups) will be explored. An additional analysis with a spline version of weeks will be carried out which uses *week* as a continuous variable allowing one to estimate the rate of change in BFI.

A secondary analysis with BFI will also be carried out which investigates the difference in proportion of fatigued subjects ( $BFI \geq 4$ ) across the three study arms. The analytical framework will be that of a mixed-effects logistic regression model with presence of fatigue ( $BFI \geq 4$  yes/no) being the dichotomous outcome. Apart from group, week, and group-by-week interaction as primary covariates, the model will also be adjusted for baseline status of severity. Remaining covariates in the model are identical to those in the continuous BFI model. The clustering effect due to subject will be accounted for using a generalized estimating equations approach under a generalized linear mixed models framework.

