## 9.0 STATISTICAL METHODS

**Power Analysis.** Our power analysis is based on our primary aim to, “Examine the effect of 6 weeks of daily self-administered relaxing acupressure compared to self-administered sham acupressure or no treatment on persistent fatigue as measured with The Brief Fatigue Inventory.” Although we will run a larger model for the analysis, in the power calculation we focus on the specific components of the model in which we are interested. Towards that end, we compute the power via simulation using a mixed effects model with a between-subject factor group (3 levels), a within-subject factor week (0, 6, 12, and 24), group-by-time interaction and a random subject effect. The mean BFI at baseline is assumed to be 5.5, whereas values at end of treatment were assumed to be 4.5, 3.5, and 2, respectively for no treatment, sham acupressure and relaxing acupressure arms. The between-subject variance is assumed to be 4 at all time-points whereas the variance of the random subject component is taken to be 4 also (yielding an intra-class correlation of 0.5). These assumed values are estimates based on our pilot data. For this configuration, the power for detecting a significant week-by-group interaction is greater than 95% with a sample size of 50 evaluable participants per treatment arm (we anticipate a ~13 % drop out with the goal of 150 completers for a total sample size of 171) and a 5% level of significance. Such a model is able to detect a post-hoc difference between the relaxing acupressure and each of the other two arms with more than 90% power at a reduced 0.01 level of significance in order to protect against Type I error probability inflation. In the second phase after the treatment period, it is anticipated that both the no-treatment and the sham acupressure arms will experience a bounce

back close to the baseline level, while the relaxing acupressure arm will maintain its end-of-treatment average. Thus, the differences will be more pronounced than those in the active treatment phase, and we will be well

powered to detect the effect size.

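### The primary model adjusts only for stage, in a form that cannot sharpen the group-by-week contrast; conditioning on week-0 BFI and adding the depression and activity data already collected would

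*Combined protocol and SAP*

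**What the plan says.** Section 1.0 (Background and Significance) states that risk of fatigue after cancer treatment "does not appear to be associated with type of cancer, cancer treatment, stage of diagnosis or histopathology of the cancer", and points to host factors instead, giving depression and level of physical activity as examples. Under Descriptive/Baseline Variables, the activity questionnaire (IPAQ) is justified because "physical activity is known to impact the presence and severity of cancer-related fatigue and sleep disturbance". Table 2 in Section 4.1 schedules both IPAQ and the PROMIS battery, which includes the depression short form, at week 0.

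The Statistics Section specifies a linear mixed model for BFI. Week has four levels (0, 6, 12, 24), there is a random subject effect, and the group-by-week interaction is the effect of interest. "The covariate cancer stage at diagnosis" and its interaction with group are the only further terms. The secondary logistic model for BFI of 4 or more also adjusts for baseline severity; the primary model does not. The secondary and exploratory outcomes use analogous models.

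**The concern.** The plan adjusts for a factor that its own background describes as apparently unrelated to fatigue. It leaves out two factors that the background names as related and that every woman reports at week 0. No reason is given for the choice.

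The form of the adjustment matters as much as the choice. Week 0 is one of the outcome levels, so the group-by-week contrast is in effect a comparison of changes. A term that shifts a woman's BFI equally at every visit drops out of a change. Stage and group-by-stage are entered in that way. What is at stake is precision for the relaxing-versus-sham comparison, the smaller of the two differences for the relaxing arm.

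**Working it through.** **Inputs (Section 9.0, Power Analysis).** "The mean BFI at baseline is assumed to be 5.5" in all arms; "values at end of treatment were assumed to be 4.5, 3.5, and 2" for no treatment, sham and relaxing acupressure. There are 50 evaluable women per arm. Subject variance is 4, and the other variance of 4 is read as residual, because only that gives the stated intra-class correlation of 0.5. Total variance is then 8. The interaction is tested at "a 5% level of significance" and the pairwise comparisons at 0.01, taken as two-sided. The documents give no correlation between BFI and depression or activity, so those below are assumptions.

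**1. The plan's own figure.** Mean changes are −1, −2 and −3.5, with mean −2.167. The squared deviations sum to 1.361 + 0.028 + 1.778 = 3.167. The variance of a change is 2 × 4 = 8, so the noncentrality is 50 × 3.167 / 8 = 19.79. Power of the F test on weeks 0 and 6 is about 98%. The claim that "the power for detecting a significant week-by-group interaction is greater than 95" percent is reproduced.

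**2. The relaxing-versus-sham contrast at week 6.** The difference is 3.5 − 2 = 1.5. SE = √(2 × 8 / 50) = 0.5657. Power at 0.01 is 51% (t distribution) or 53% (normal approximation). The stated "more than 90% power at a reduced 0.01 level of significance" is therefore not reached on this contrast alone. It is reached over all four visits with the plan's assumed rebound in the other two arms.

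**3. Time-constant covariates in the planned model.** Let a baseline covariate explain 10% to 50% of subject variance and enter as a main effect.

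| Setting | SE without | SE with (10%, 30%, 50%) |
|---|---|---|
| 50 per arm, complete | 0.5657 | 0.5657, 0.5657, 0.5657 |
| 57 per arm, 13% dropout | 0.5603 | 0.5598, 0.5586, 0.5571 |

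The gain is exactly zero with complete data and at most 0.6% with 13% dropout. With 20% dropout it is at most 0.9% (0.5799 to 0.5747). The cancellation applies equally to stage.

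**4. Conditioning on week-0 BFI.** Residual variance at week 6 is 8 × (1 − 0.5²) = 6, a reduction of (8 − 6)/8 = 25%. SE = √(2 × 6 / 50) = 0.490. Power for 1.5 points at 0.01 is 67% (t) or 69% (normal).

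**5. Adding a covariate to that model.** With correlation ry with week-6 BFI and rx with week-0 BFI, the further share of residual variance removed is (ry − 0.5 rx)² / [0.75 (1 − rx²)].

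| ry | rx = 0.5 | rx = 0.3 |
|---|---|---|
| 0.3 | 0.4% | 3.3% |
| 0.4 | 4.0% | 9.2% |
| 0.5 | 11.1% | 17.9% |

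At rx = 0.5, power (t) rises from 66.8% to 69.0% when 4% is removed and to 73.1% when 11% is removed. Without the covariate, the same power needs 52 and 56 women per arm, so the gain is worth 2 and 6 women per arm. The top corner (17.9%) needs a covariate that predicts week-6 BFI as well as week-0 BFI does, but is only weakly related to week-0 BFI. It should not be relied on.

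**6. Downside of crossing with week.** In the planned model, a covariate that predicts level but not change raises the SE from 0.5657 to 0.5675 when crossed with week, about 0.3%.

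**The case against.** A reader might infer that leaving out depression and activity loses precision in the model as written. Step 3 shows that it does not. A reader might also infer that chance imbalance in these factors distorts the result. Imbalance in something that shifts only the level of fatigue cancels from the change contrast. The documents link both factors to the presence and severity of fatigue, not to change or response.

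A third inference is that stage is useless and should be replaced. The documents do not support that either. Section 3.2 describes block stratified randomisation without naming the strata, so stage may be one of them. Group-by-stage may be meant to examine effect modification. The background wording is hedged and concerns fatigue after treatment, whereas eligibility admits stages I to IV and requires only that primary treatment has been initiated. The pilot analysis also adjusted for stage.

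Other objections stand in part. Most of the gain comes from conditioning on week-0 BFI. Excluding untreated mood disorder, and requiring BFI of at least 4, may weaken the correlations. Table 3 gives a pooled change SD of about 1.73. At that SD, power for 1.5 points at 0.01 in the planned contrast is already about 95%, and a further 4–11% cut in variance takes it only to 96–97%. However, the observed true-versus-sham difference in that table is 0.66, where precision still matters.

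Finally, Section 9.2 and Tables 3 and 4 report week-6 changes by arm. The documents do not name their source, but the arms match this trial. If these are its results, changing the primary model now would no longer be prespecified.

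**Conclusion.** The point holds as a question of efficiency and internal consistency. The covariate choice is unexplained and sits poorly with the background, and the form of adjustment cannot improve the contrast of interest when data are complete.

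Conditioning on week-0 BFI would cut the week-6 contrast variance by about 25%, given the plan's intra-class correlation of 0.5. Depression and activity add a remainder of about 0–3% at an assumed week-6 correlation of 0.3, and about 4–11% at 0.4–0.5 with a week-0 correlation of 0.5. The percentages scale with the correlations. The power figures also rest on residual variance 4: if 4 were the total variance, the planned contrast would have about 87–88% power, and 95–96% after conditioning on baseline.

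Randomisation keeps the treatment comparison valid without any of this, so it is an inexpensive improvement and not a source of bias.

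**What to change.** In the Statistics Section, condition the primary model on week-0 BFI, either as a covariate or as a baseline constrained to be equal across arms, with weeks 6, 12 and 24 as the outcomes; name one form. Add the week-0 PROMIS depression T-score and week-0 IPAQ activity, each crossed with week, and fix the IPAQ scale (for example capped or logged) in advance. Use week-0 values only, since later depression scores are outcomes.

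Keep stage, certainly if it is a randomisation stratum, and state why it is there. Name the strata in Section 3.2.

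The cost is SAP wording, a few degrees of freedom and one decision about the IPAQ scale. No new data are needed, and the planned chained-equation imputation already covers missing covariates. If outcome data by arm have already been seen, report the revised model as a labelled supportive analysis beside the planned one.
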